Objectives	To demonstrate that coordination of HBO with SRS treatments is feasible. To demonstrate that outcomes for patients treated with combination of HBO and SRS are non-inferior to historical controls.
Number of Subjects	20 evaluable participants
Diagnosis and Main Inclusion Criteria	Patients with brain metastases referred for SRS
Study Product, Dose, Route, Regimen	Hyperbaric oxygen given at 2.4 ATA for 30 minutes immediately prior to SRS
Duration of administration	HBOT for 30 minutes
Reference therapy	SRS without prior HBO
Statistical Methodology	Prospective Phase-I trial (“proof-of-principle”) with matched historical controls

1 Introduction

This document is a protocol for a human research study. This study is to be conducted according to US and international standards of Good Clinical Practice (FDA Title 21 part 312 and International Conference on Harmonization guidelines), applicable government regulations and institutional research policies and procedures.

1.1 Background

Hyperbaric oxygen (HBO) treatment, in which patients breathe 100% oxygen at a high ambient atmospheric pressure, is an appealing strategy for overcoming tumor hypoxia. HBO dramatically increases the oxygen dissolved in blood plasma, which in turn increases oxygen delivery to tissue.

Radiation therapy is the standard of care for the treatment of many malignancies, including brain metastases. Its mechanism of action includes interaction with dissolved molecular oxygen, formation of oxygen radicals, and consequent damage of nuclear DNA. For this reason, hypoxic tissues are less sensitive to radiation damage, both *in vitro* and *in vivo* (Figure 1, Figure 2). This increase in radiation sensitivity is quite profound: two- to three-fold between hypoxic and oxic tissues (an “oxygen-enhancement ratio” – OER – between 2 and 3) (Figure 1). In contrast, oxygen’s radiation sensitizing effect flattens at higher pO₂ levels, with little additional sensitization above pO₂ levels of 20-30 mm Hg (Figure 3).

Figure 1. Oxygen enhances radiosensitivity of cells growing *in vitro*. From Hall 2012, page 88 [1].

[figure not shown]

Figure 2. Oxygen enhances radiosensitivity of cells irradiated *in vivo*. The “Air Curve” represents data for cells from tumors irradiated in mice breathing air (a mix of hypoxic and oxic cells). The “Hypoxic Curve” represents data for cells from tumors irradiated in mice breathing pure nitrogen (all cells hypoxic). The “Oxic Curve” is for cells irradiated *in vitro* in oxygen (all cells oxic). From Hall 2012, page 95 (data courtesy of [name] – see citations listed in Hall) [1].

[figure not shown]
[figure not shown]

Figure 3. Dependence of radiosensitivity on oxygen concentration, as summarized by Eric Hall. Note that most of this change in radiosensitivity arises between 0 and 30 mm Hg. There is virtually no additional sensitization at pO₂ levels above 155 mm Hg (normal levels in air). From Hall 2012, page 90 [1].

Thus, HBO offers the potential advantage of increasing the radiation sensitivity of hypoxic tissues (e.g. tumors with poor blood supply) by raising their pO₂ levels (even if only by a relatively small amount, increasing radiosensitivity disproportionately), while having little additional effect on surrounding normal tissues. These normal tissues have normal oxygenation and blood supply, so suffer little additional radiosensitivity if their pO₂ levels are increased.

Experimental data support the potential radiosensitizing effect of HBO in intracranial tumors (characterized by large hypoxic fractions) while having little effect on normal tissues (with normal oxygen levels). Four clinical trials have evaluated the radio-sensitizing potential of hyperbaric oxygen in malignant gliomas. This technique was found to be feasible [2], involved minimal toxicity on normal tissues [3, 4], and improved outcomes [5, 6]. A recent review of hyperbaric oxygen as a radiosensitizer concluded, “... *given the findings of improved tumor control and mortality..., there is a case for large randomized trials of high methodological vigor...*” [7].

Although HBO has been studied in conjunction with XRT in the treatment of primary brain tumors, no prior study has examined the role of HBO in combination with XRT in the treatment of tumors (“secondary”) metastatic to the brain. Furthermore, no prior study has studied HBO in conjunction with stereotactic radiosurgery (SRS).

Characterized by the delivery of millimeter-accurate, high-dose radiation therapy in a single fraction to a small volume of target tissue, SRS is the standard of care for the

treatment of small brain metastases. It is safe and efficacious in a wide variety of clinical situations. Local control rates at one year following SRS range from 50-90%, with tumor size a significant prognostic factor (Figures 4 and 5).

Figure 4. Kaplan-Meier analysis of freedom-from-local recurrence (LR) stratified by tumor size for a large population of patients with intact brain metastases treated with SRS [8].

[figure not shown]

FIG. 1. Graph showing cumulative tumor progression-free survival curves, based on tumor size. The maximum lesion diameters are provided. The mean prescribed doses were 20.6 Gy in 8573 tiny, 20.3 Gy in 977 small, 19.2 Gy in 441 medium, and 15.7 Gy in 172 large lesions. The tumor control rates at 1 year were 99.5% in tiny, 92.6% in small, 87.3% in medium, and 65.5% in large lesions. Differences were statistically significant ($p < 0.0001$).

Figure 5. Kaplan-Meier analysis of freedom-from-local recurrence (LR) stratified by pre-operative tumor diameter at 3.0 cm: recent DHMC experience [9].

[figure not shown]

Table 1. One-year and two-year outcomes stratified by tumor size: recent DHMC experience [9].

Table 1 Incidence as a function of tumor size

Parameter	% for all subjects		% of subgroup with tumors below or above cutoff size of 3.0 cm				% of subgroup with tumors below or above cutoff size of 2.0 cm			
	1 y	2 y	Below or equal to 3.0 (n=29)		Above 3.0 (n=20)		Below or equal to 2.0 (n=15)		Above 2.0 (n=34)	
			1 y	2 y	1 y	2 y	1 y	2 y	1 y	2 y
Overall survival	52.5	31.7	51.3	36.0	55.0	30.0	69.2	49.5	46.6	25.1
Free of LR	85.5	66.9	89.1	89.1	80.7	40.4	100.0	100.0	79.2	51.3
Free of DR	43.8	24.4	50.0	36.4	35.6	8.9	81.8	65.5	31.5	10.5
Free of ICR	41.4	17.7	45.4	31.1	35.6	5.9	81.8	65.5	28.3	4.2
Free of WBRT	58.4	37.3	75.9	65.0	39.9	13.3	100.0	100.0	44.5	20.0

Abbreviations: DR = distant recurrence; ICR = intracranial recurrence (LR or DR); LR = local recurrence; WBRT = whole-brain RT.

Data show estimated 1- and 2-year percentages above and below 3.0 cm (median) and above and below 2.0-cm tumor diameter for the entire sample and for subgroups defined by tumor diameters.

In this trial we will use hyperbaric oxygen as a radiosensitizer prior to stereotactic radiosurgery (SRS) for brain metastases. We hypothesize that reducing tumor hypoxia with HBO will increase the sensitivity of these tumors to SRS, that this clinical benefit should increase with lesion size, and that no significant radiosensitizing effect of HBO will

arise in the surrounding normal brain tissues.

We postulate these hypotheses due to several well-known laboratory phenomena, as demonstrated in the research studies of [name] (co-investigator on this project) and of other investigators:

- tumors are hypoxic;
- HBO increases tissue oxygenation;
- increasing pO_2 levels above hypoxic levels ($pO_2 > 3$ mm Hg) increases radiosensitivity with an OER between 2 and 3;
- this OER effect flattens above 20-30 mm Hg (limiting toxicity in normal tissues).

Several clinical observations also support these hypotheses:

- SRS delivers dose with millimeter accuracy to target tissues, limiting normal tissue toxicity;
- efficacy of SRS for tumors metastatic to the brain decreases when treating larger metastases – for example, >30% local recurrence risk at one year after SRS for lesions >3 cm in diameter versus <20% for lesions <2 cm [8] (Figure 4);
- efficacy of SRS decreases when treating larger resected lesions – for example, DHMC experience demonstrated 51% local control rate observed at two years for resected lesions with diameters greater than 2.0 cm versus 100% local control rate observed for diameters less than 2.0 cm [9] (Table 1).

If effective, this innovative approach to the treatment of brain metastases may offer patients improved tumor control and quality of life without increased treatment risks.

1.2 *Investigational Agent*

⇒ Hyperbaric oxygen treatment given at 2.4 ATA for 30 minutes followed by radiation therapy

Hyperbaric oxygen is oxygen under pressure delivered within a specially designed chamber (hyperbaric chamber). During hyperbaric treatment the patient receives oxygen while resting supine inside the hyperbaric chamber. This increases the oxygen content of blood markedly, not by increasing hemoglobin saturation, since hemoglobin is already highly saturated breathing room air, but by increasing the oxygen dissolved in blood plasma. This increase in partial pressure of oxygen (pO_2) in blood increases the pO_2 commensurately within both normal and tumor tissues.

1.3 *Preclinical Data*

As discussed in Section 1.1, over the past five decades molecular oxygen has been proven to be a powerful modifier of cellular radiation sensitivity [10]. The cytotoxic effect of ionizing radiation is increased three-fold when irradiation is performed under well-oxygenated conditions compared to anoxic conditions (the “oxygen-enhancing ratio” or OER) [11].

1.4 Clinical Data

Recent reviews have summarized the use of hyperbaric oxygen as a radiation sensitizer [7, 12, 13].

Several investigators have demonstrated hypoxic regions within brain tumors of patients [14-16]. Likewise, many studies have demonstrated significant hypoxia within both primary and metastatic tumors in a wide variety of animal and human models.

HBO treatment addresses this issue. Intratumoral oxygen levels remain elevated for about 30 minutes after exposure to hyperbaric oxygen; however, intratumoral pO₂ in the presence of 100% normobaric oxygen does not increase either intra- or peritumoral pO₂ [17].

Older clinical studies of HBO as radiosensitizer demonstrated positive results. For example, in 1997 Machin and colleagues summarized 30 years of the U.K.'s Medical Research Council trials of solid tumors, an experience that included five trials comparing standard therapy in air against standard therapy in hyperbaric oxygen [18]. Of these five trials, two demonstrated highly significant advantages for patients receiving HBO (both studies in head-and-neck cancer), two did not demonstrate a significant survival advantage for HBO (one bladder and one cervix trial), and one demonstrated a strong trend for a survival advantage for HBO (also in cervical cancer patients). The authors concluded: "Thus, the five trials of HBO, when taken together, established a conclusive survival advantage over standard radiotherapy in air and give a pooled HR [hazard ratio] = 0.80 (95% CI 0.68-0.94)."

Conducted in the mid-1970s, a trial of 48 head-and-neck cancer patients at Yale-New Haven randomized subjects to receive radiotherapy with or without HBO [19]. Although interpretation of the results was severely limited due to several technical factors, including the use of large radiation fraction sizes (two fractions of 12.65 or 11.70 Gy, the former without HBO, the latter with HBO), long-term outcomes demonstrated a highly significant difference in complete clinical response with the addition of HBO (even in combination with the lower XRT dose): 21/25 in the HBO arm, 13/25 in the control arm. Long-term severe late complications were not significantly different between the two groups (though excessive in both arms, due to the large fraction sizes). This study exemplifies the difficulties of most early trials of HBO: poor radiotherapy techniques confounded potential improvements in outcomes [13].

More recent trials using hyperbaric oxygen prior to radiation therapy have shown promising results. In a non-randomized study in 1999, Koshi et al. demonstrated improved median survival in patients with high-grade gliomas who received hyperbaric oxygen prior to radiation compared to patients who were treated with standard radiation therapy and chemotherapy alone (24 months versus 12 months) [20]. Beppu et al. studied hyperbaric oxygen prior to radiation therapy in patients with malignant high-grade gliomas who were also treated with interferon-beta and nimustine hydrochloride. Progression-free survival in their patients with glioblastoma multiforme was 9.5 months, which compares favorably with the 6.9 months in a recent trial of temozolomide combined with radiation therapy [3].

Ogawa et al. recently published long-term follow up data from their successful Phase II trial which ran from 2000-2006 [6].

In a 2007 review of hyperbaric oxygen as a radiation sensitizer, Overgaard concluded, "...ample data exist to support a high level of evidence for the benefit of hypoxic modification [21]." In a recent meta-analysis of HBO in head-and-neck trials [11] Overgaard found the odds ratio between HBO and control treatments to be 0.46 (CI 0.33-0.64, p<0.001).

In a contemporary Phase-I multi-institutional trial studying the addition of HBO as radiosensitizer for the treatment of head-and-neck cancer, currently reported in abstract form [22], DHMC established a successful record for coordinating HBO with fully fractionated radiation delivery (average time from chamber to "beam on" of approximately 8 minutes), in conjunction with standard radiation doses delivered five days a week over seven weeks. No excess toxicity was observed among these patients.

Extending this experience, our current study will explore the safety of the novel combination of HBO followed by SRS for brain metastases.

1.5 Dose Rationale and Risk/Benefits.

Dose Rationale: Hyperbaric oxygen will be given at 2.4 ATA, the dose that was used previously in our phase I head and neck cancer study. This is the dose of oxygen generally used for the treatment of radiation complications. Also, this dose is consistent with the doses used in several previous studies, although this level is not as high as was used in some of the prior glioma studies (2.8 ATA). In short, this dose has been shown in our own work and that of others to be safe.

Risks: The main risks of hyperbaric oxygen therapy are barotrauma to the ear, claustrophobia, and oxygen-induced seizures. Ear barotrauma, if it occurs, is not life threatening and resolves with time. Patients with claustrophobia requiring treatment will be offered lorazepam to help with confinement anxiety and will have the opportunity to experience the hyperbaric chamber prior to the treatment day. Patients are at small risk for increased seizure activity since high oxygen levels can produce seizures, although usually at levels higher than planned for this study. For the level of oxygen used in this study (2.4 ATA) the incidence in the general population receiving HBOT is about 0.06% or 6 per 10,000 dives [23].

HBO may also contribute to the risk of radiation-related complications. In his review and meta-analysis of hypoxic modification of radiotherapy in head-and-neck cancer patients, Overgaard identifies eight trials that studied HBO in comparison to normal treatment controls. These showed a significant increase in the risk of radiation-related complications, with an odds ratio of 2.43 (CI 1.43-4.12, p<0.01). However, Overgaard hastens to add that the late tissue damage observed with HBO arose in trials where the radiation technique was – even absent HBO – known to have a relatively high likelihood of late toxicity; and the difference in some of the trials was further exacerbated by administering high doses per fraction in the HBO arm but conventional doses per fraction

in the control arm, further confounding the results. Overgaard concludes, “Consequently, there is no definitive evidence of any excess morbidity associated with the [HBO] hypoxic modification itself...” [11]

Risk/Benefit Summary: This is a study for patients with brain metastases. These patients are at significant risk for tumor recurrence. Treatment options for these patients are limited. The results of this investigation may provide information for improved treatment of other patients with this disease. Treatment with hyperbaric oxygen is safe, but nevertheless there is the very small risk for seizures and barotrauma to the ear. Also, the theoretical potential risk exists that the combination of HBO with radiation therapy may increase late tissue damage from radiation exposure – although there is no solid clinical evidence of this potential risk, while there is good radiobiological data that HBO does not contribute significantly to the radiation sensitivity of tissues that are already well-oxygenated, such as normal brain.

2 Study Design

2.1 General Design

This is a Proof of Principle study of hyperbaric oxygen as a radiation sensitizer prior to radiosurgery for brain metastases.

2.1.1 Study Objectives

Primary Objective: To demonstrate that coordination of HBO with SRS treatments is feasible.

Secondary Objective: To demonstrate that outcomes for HBO combined with SRS treatment are non-inferior to historical controls.

2.1.2 Study Flowchart

The duration of the study is 5 years. The study flowchart encompasses three sequential phases for each participant: (1) pre-treatment preparations for both HBO and SRS, (2) treatment with HBO immediately followed with SRS; (3) post-treatment follow-up including history and physical exam, brain MRI, and QOL instruments initially 4 to 6 weeks after treatment and then every 3 months for a minimum of 1 year. See Figure 6.

Figure 6. Study Flowchart

2.2 Primary Study Endpoints

Demonstrate that coordination of HBO with SRS treatments is feasible.

For HBO sensitization of SRS patients to be feasible, patients must receive radiation treatment within a time frame in which pO₂ levels are meaningfully elevated. Since intratumoral oxygen levels within the brain remain elevated for about 30 minutes after exposure to hyperbaric oxygen [17], feasibility of HBO-SRS treatment requires that a patient at least begin SRS within 30 minutes of leaving the HBO chamber. Evaluation of the ability to achieve this goal will be the primary study endpoint. We will measure time from end of “dive” to start of SRS treatment. Goal will be to achieve “beam on” within 15 minutes of leaving the chamber. Total time for treatment to one isocenter (from first arc’s beam-on to last arc’s beam-off) using SRS in this study is estimated at 10 minutes (three SRS arcs, each 2 minutes, plus set-up time between the first and second and between the second and third arcs, each 2 minutes, totaling 10 minutes). We anticipate a learning-curve as HBO and therapy staff to develop skill sets for optimizing time across the various steps of the procedure:

- Leaving the HBO chamber
- Fitting the - [VisionRT open face mask system](#)
- Positioning the patient on the table
- Imaging the patient to confirm position
- Reviewing/approving images for treatment

2.3 Secondary Study Endpoints

Demonstrate that outcomes for HBO combined with SRS treatment are non-inferior to historical controls.

Secondary endpoints will include:

- Symptomatic treatment toxicity. Every patient who receives treatment on this protocol will be evaluated for solicited adverse events. “Solicited adverse events” are predefined side effects/medical occurrences identified by the PI and co-PIs to be potentially related to intracranial SRS and/or HBO treatments. These are enumerated in Attachment 14.6. These will be graded using the

Common Toxicity Criteria Adverse Events (CTCAE) v4.0 of the National Cancer Institute. These will be analyzed in one of two categories:

- Acute toxicities
 - Neurological toxicities
 - Other toxicities
- Chronic toxicities
 - Neurological toxicities
 - Other toxicities
- Radiographic evidence for radionecrosis/treatment effects in normal tissue, as defined by review/analysis by diagnostic radiologist of follow-up MRI imaging
- Incidence of whole brain radiation therapy (WBRT)
- Incidence of repeat SRS to the index site
- Incidence of repeat SRS to a distant site
- Local disease recurrence at the treatment site, as defined by review/analysis by diagnostic radiologist of follow-up MRI imaging
- Distant disease recurrence elsewhere in the brain, as defined by review/analysis by diagnostic radiologist of follow-up MRI imaging
- Overall survival

Radiographic MRI outcomes will be assessed by a diagnostic radiologist using standard criteria for radiation treatment effects and disease recurrence. Imaging sets will typically include T1-weighted sequences (with and without gadolinium), T2- and Flair-weighted sequences, and also perfusion, ADC ("apparent diffusion coefficient"), and spectroscopic imaging studies.

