All solicited adverse events that do not meet any of the criteria for serious will be regarded as **non-serious solicited adverse events**.

Adverse Event Reporting Period

The study period during which solicited adverse events must be reported is defined as the period from the initiation of any study procedures to the end of the study treatment

follow-up. For this study, the study treatment follow-up is defined as the time following study treatment until the date of documented death, withdrawal of consent, or the end of the study, whichever occurs first.

Preexisting Condition

A preexisting condition is one that is present at the start of the study. A preexisting condition will be recorded as a solicited adverse event if the frequency, intensity, or the character of the condition worsens during the study period.

General Physical Examination Findings

At screening, any clinically significant abnormality will be recorded as a preexisting condition. At the end of the study, any new clinically significant findings/abnormalities that meet the definition of an adverse event must also be recorded and documented as an adverse event.

Post-study Adverse Event

All unresolved solicited adverse events will be followed by the investigator until the events are resolved, the subject is lost to follow-up, or the solicited adverse event is otherwise explained. At the last scheduled visit, the investigator will instruct each subject to report any subsequent event(s) that the subject, or the subject's personal physician, believes might reasonably be related to participation in this study. The investigator will notify the study sponsor of any death or adverse event occurring at any time after a subject has discontinued or terminated study participation that may reasonably be related to this study. The sponsor will also be notified if the investigator becomes aware of the development of cancer or of a congenital anomaly in a subsequently conceived offspring of a subject that has participated in this study.

Abnormal Laboratory Values

A clinical laboratory abnormality will be documented as an adverse event if any one of the following conditions is met:

- The laboratory abnormality is not otherwise refuted by a repeat test to confirm the abnormality
- The abnormality suggests a disease and/or organ toxicity

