7.2 Recording of Adverse Events

At each contact with the subject, the investigator will seek information on solicited adverse events by specific questioning and, as appropriate, by examination. Information on all solicited adverse events will be recorded immediately in the source document, and also in the appropriate adverse event module of the case report form (CRF). All clearly related signs, symptoms, and abnormal diagnostic procedures results should be recorded in the source document, though should be grouped under one diagnosis. These will be graded using the Common Toxicity Criteria Adverse Events (CTCAE) v4.0 of the National Cancer Institute. Retrospective review of patient charts will be employed to assure accurate recording of solicited adverse events. Any additional solicited adverse events identified by such retrospective review will be incorporated into the data base and included in the analysis.

All solicited adverse events occurring during the study period will be recorded. The clinical course of each event will be followed until resolution, stabilization, or until it has been determined that the study treatment or participation is not the cause. Serious adverse events that are still ongoing at the end of the study period will be followed up to determine the final outcome. Any serious adverse event that occurs after the study period and is considered to be possibly related to the study treatment or study participation will be recorded and reported immediately.

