7.4 Stopping Rules

An internal stopping rule is set in place whereby the study will be terminated if (1) feasibility appears unattainable, or (2) a significant number of patients experience a significant adverse event (SAE) as outlined above:

- Regarding the primary endpoint of feasibility, we anticipate a steep learning curve for treatment of patients on this trial. The overall goal is to begin SRS within 15 minutes of exiting the HBO chamber; however, it is known that oxygen levels remain elevated in the brain up to 30 minutes after HBO treatment. The following stopping rules will be applied:
 - Analysis after enrollment of first 10 patients demonstrates no more than two patients (20%) treated within 30 minutes of HBO chamber exit.
 - Analysis after enrollment of first 15 evaluable patients demonstrates no more than five patients (33%) treated within 30 minutes of HBO chamber exit.
- Regarding the secondary endpoint of noninferiority, every patient who receives treatment on this protocol will be evaluated at every patient encounter for adverse events. Toxicities will be graded using the Common Toxicity Criteria Adverse Events (CTCAE) v4.0 of the National Cancer Institute.
 - Overall incidence of adverse events in this study will be reviewed every three months.
 - At time of any such review, if more than 40% of enrolled patients (minimum of 5 patients) experience SAEs that are deemed likely related to the protocol treatment (HBO combined with SRS), then the study will be terminated (i.e. more than 2 out of 5 patients, or more than 4 out of 10 patients, for example).
 - Note that some SAEs are expected in this patient population, given the nature of the disease process that is being treated. The stopping rule of 40% was elected as representing an incidence level significantly higher than that expected routinely in this patient population.
- It is the responsibility of the Principal Investigator to oversee the safety of the study. This safety monitoring will include careful assessment and appropriate reporting of adverse events as noted above, as well as quarterly review by the Norris Cotton Cancer Center Data and Safety Monitoring and Accrual Committee (see section 9 Auditing, Monitoring and Inspecting). Medical monitoring will include a regular assessment of the number and type of serious adverse events.

8 Data Handling and Record Keeping

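### The toxicity endpoint counts every solicited adverse event to death or study end, without a relatedness condition or a split at brain recurrence or later brain treatment, so the undivided total is not toxicity of HBO-SRS

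*Combined protocol and SAP*

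**What the plan says.** Section 2.3 lists symptomatic treatment toxicity first among the secondary endpoints and fills it with solicited adverse events: "Every patient who receives treatment on this protocol will be evaluated for solicited adverse events". An event is solicited because its type is on a list "identified by the PI and co-PIs to be potentially related to intracranial SRS and/or HBO treatments". That describes a class of events and does not attribute the individual one. On analysis, 2.3 says "These will be analyzed in one of two categories", namely acute and chronic, each divided into neurological and other. It gives no day that separates acute from chronic.

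Section 7.1 starts the window at the first study procedure and ends follow-up "until the date of documented death, withdrawal of consent, or the end of the study, whichever occurs first". It also counts a pre-existing condition that worsens. Section 7.2 adds "All solicited adverse events occurring during the study period will be recorded", and on chart review: "Any additional solicited adverse events identified by such retrospective review will be incorporated into the data base and included in the analysis".

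The list in 14.6 includes headache, seizure, ataxia, cognitive disturbance, memory impairment, somnolence and intracranial hemorrhage.

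Causality is used in three other places: 7.2 lets it end the follow-up of an event, 7.3 uses it for expedited reports, and 7.4 limits the SAE stopping rule to events judged likely related.

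**The concern.** The endpoint's name claims attribution to treatment, but its derivation contains none. Take a patient with new distant brain metastases at month 7, WBRT at month 8 and memory impairment at month 11. Read literally, the plan scores this as a chronic neurological toxicity of HBO-SRS.

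Section 1.1 says that SRS has not previously been studied with HBO, and 1.4 says that the study will explore the safety of the combination. With 20 patients, a few such events change the result. They could make the combination look harmful, or make a real late effect harder to see among disease symptoms. A control comparison could remove the background, but neither list of compared events in 6.1 contains solicited events; one of them contains radionecrosis. Section 6.2 nevertheless names toxicity in its power sentence, so the use to be made of the total is unclear.

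**Working it through.** **Reading the text.** The steps that build the endpoint are in 2.3, 7.1, 7.2 and 14.6. None has a relatedness filter or a cut at recurrence, WBRT or repeat SRS. All three of those are already time-to-event outcomes in 6.1, so the dates will exist.

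**Plan's own figure.** The plan gives no expected rate of solicited events. The only power figure that mentions toxicity is the relative risk of 0.39 in 6.2. It reproduces: 20 v 20, control median 6 months, one-sided 0.05 and an assumed 24 months of follow-up give 32.0 expected events and, by Freedman's formula, a detectable ratio of 0.389. The present point does not depend on it.

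**Inputs for scale.** Table 1 (Section 1.1), at 1 y / 2 y:
- At or below 2.0 cm (n=15): free of intracranial recurrence 81.8% / 65.5%; overall survival 69.2% / 49.5%.
- Above 2.0 cm (n=34): 28.3% / 4.2%; 46.6% / 25.1%.

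Section 6.2 plans 10 patients in each size group, and 5.4 sets follow-up at two years. Recurrence and death are assumed independent, with constant monthly hazards within each year.

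**Recurrence before death.** Let r be the recurrence hazard and d the death hazard. In each year the probability is r/(r+d) times the fall in the proportion alive and recurrence-free.
- At or below 2.0 cm, year 1: r = -ln(0.818)/12 = 0.0167, d = -ln(0.692)/12 = 0.0307; 0.353 x (1 - 0.818 x 0.692) = 0.353 x 0.434 = 0.153. Year 2: r = 0.0185, d = 0.0279; 0.399 x (0.566 - 0.324) = 0.097. Sum 0.25.
- Above 2.0 cm, year 1: r = 0.1052, d = 0.0636; 0.623 x (1 - 0.132) = 0.541. Year 2: r = 0.1590, d = 0.0516; 0.755 x (0.132 - 0.011) = 0.092. Sum 0.63.
- Planned mix: (0.25 + 0.63)/2 = 0.44, about 9 of 20 patients.

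**First solicited event.** Let h0 and h1 be the monthly first-event hazards before and after recurrence (assumed). Let a be the proportion alive, recurrence-free and event-free, and b the proportion alive after recurrence and event-free. Then a' = -(r+d+h0)a and b' = ra - (d+h1)b. Over 24 months, events before recurrence are the integral of h0·a and events after it the integral of h1·b. The excess part is the share after recurrence times (1 - h0/h1). For the 10/10 mix:

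| h0 / h1 per month | First event before | First event after | Share after | Excess part |
|---|---|---|---|---|
| 2% / 4% | 17.1% | 12.9% | 43% | 0.43 x 0.50 = 21% |
| 2% / 8% | 17.1% | 20.1% | 54% | 0.54 x 0.75 = 41% |
| 4% / 8% | 29.5% | 18.1% | 38% | 0.38 x 0.50 = 19% |
| 4% / 4% | 29.5% | 11.6% | 28% | 0% |

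Of 20 patients, 11.6% to 20.1% is about 2 to 4 whose first scored event comes only after recurrence. The model counts first events from treatment onward, with no acute window, because the plan defines none.

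**The case against.** Recording every event on a fixed list, whatever its cause, is sound practice in an open-label study because it avoids subjective attribution. That stands, and the all-events table should stay. Treatment-specific late injury also has its own radiologist-read radionecrosis endpoint, so a real late effect is not simply lost. Because the dates are collected, the split could be made later. These points limit the harm, but none makes the undivided total a measure of treatment toxicity, and a split chosen after the data are seen is weaker than a planned one.

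Three stronger readings are tempting, and the documents do not support them.
- *The protocol makes no causal attribution at all.* Sections 7.2, 7.3 and 7.4 do; the gap is in this endpoint only.
- *The chronic neurological figure mostly reflects progression.* The all-subjects row of Table 1 gives 55% recurring before death and 39-66% of scored patients with a first event only after recurrence. But that row has 34 of 49 patients above 2.0 cm, against a planned 10 of 20. Its lower end comes from equal hazards, where recurrence adds no risk. With the planned split, the excess part does not exceed 41% in any scenario.
- *Events before recurrence should be the main result.* That is debatable: 1.5 names late tissue damage as the theoretical risk, and radionecrosis can first be read as recurrence.

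**Conclusion.** The concern holds for the endpoint as derived in 2.3: it labels as treatment toxicity a count that includes events after brain recurrence and later brain treatment, with neither relatedness nor timing to separate them. In the planned size mix, about 44% of patients would recur in the brain before death by 2 years. About 28-54% of scored patients would have their first event only after recurrence, and 0-41% of scored patients would owe that event to excess risk after recurrence.

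The 44% rests on a small series (n=49) of resected lesions, while half the trial has intact lesions, and on independence of recurrence and death. The other two ranges also rest on assumed event rates that no document supplies. The structural gap does not depend on any of these figures. This is a worthwhile, cheap improvement; it does not show that the safety result would be mainly disease.

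**What to change.** In 2.3 and 6.1:
- Keep the table of all solicited events.
- Present chronic toxicity in two columns, onset before and onset after the first of intracranial recurrence, WBRT or repeat SRS, with time at risk for each period. State the day from which an event counts as chronic.
- Record the investigator's relatedness judgment for every solicited event, serious or not.
- State that the undivided total is not to be described as toxicity of HBO-SRS.

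The cost is some wording, one more table and one more data field; the dates are already collected. The drawback is that symptoms of radionecrosis first read as recurrence fall in the after column, which is why the all-events table stays.
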